7.0 PATIENT DISPOSITION

The number and percentage of patients in the mITT and Safety populations will be summarized by treatment group and by study center respectively.

Screen-failure patients (ie, patients screened but not randomized) and the associated reasons for failure to randomize will be tabulated overall for all screened patients. The number and percentage of patients who complete the DBTP, patients who prematurely discontinue from the DBTP and patients who enter the safety follow-up period will be presented for each treatment group and pooled across treatment groups for all randomized patients. The reasons for premature discontinuation during the DBTP as recorded on the disposition pages of the electronic case report forms (eCRFs) will be summarized (number and percentage) by treatment group for all randomized patients.

7.1 PROTOCOL DEVIATIONS

Protocol deviations will be defined in Protocol Deviation Requirement Specification, including the classification of significance vs. non-significance. The number and percentage of patients with significant protocol deviations will be summarized by treatment group for all randomized patients. A listing for all significant protocol deviations will be provided.

8.0

DEMOGRAPHICS AND OTHER BASELINE CHARACTERISTICS

Demographic parameters (age; race; ethnicity; sex), baseline characteristics (weight; height; and body mass index, calculated as weight [kg]/(height [m])²) will be summarized descriptively by treatment group for the mITT population.

Medical and surgical histories, and psychiatric history will be coded using the Medical Dictionary for Regulatory Activities (MedDRA) dictionary and summarized by treatment group for the Safety Population.

Prior medication is defined as any medication taken before the date of the first dose of randomized IP. *Concomitant medication* is defined as any medication taken on or after the date of the first dose of randomized IP. Concomitant medications started after the last visit of the DBTP will not be included in the summaries. If any medication is taken before the date of the first dose of randomized IP and continues after initiation of randomized IP, it will be considered as both a prior and concomitant medication. The *World Health Organization (WHO) Drug Dictionary Enhanced* will be used to code medications.

Both prior and concomitant medication use, and previous treatment with psychotropic medication will be summarized by treatment group and Anatomical Therapeutic Chemical (ATC) code for the Safety Population.

Nondrug psychiatric treatment will be summarized by treatment group for the Safety Population.

9.0

EXTENT OF EXPOSURE AND TREATMENT COMPLIANCE

9.1

EXTENT OF EXPOSURE

The total number of IV doses actually received by a patient during the double-blind treatment period will be summarized by treatment group for the safety population.

IV administration notes including site reaction at placement of IV, reaction to adhesive, infusion interruption, failure of administration device, perceptual disturbances or other conditions based on mental status assessment are collected. For each item, the number and percentage of patients who had a 'yes' response will be summarized by treatment group and visit for the Safety Population.

Duration of follow-up during the DBTP will be summarized in terms of treatment duration, calculated as the number of days from the date of the first dose of randomized IP received to the date of the last dose received, inclusive. Descriptive statistics (number of patients, mean, SD, median, minimum, and maximum) will be presented by treatment group.

9.2

MEASUREMENT OF TREATMENT COMPLIANCE

Dosing compliance for the DBTP is defined as the total number of IV doses actually received by a patient during that period divided by the number of IP doses that were expected to be received during the period, multiplied by 100, regardless if a patient discontinued from the study. The number of expected doses for a patient is defined as the number of the days from the first dose to the exit visit divided by 7 and rounded up the next integer with the upper limit of 6.

10.0 EFFICACY ANALYSES

All efficacy analyses will be based on the mITT Population, unless stated otherwise. The baseline for each specific efficacy endpoint is defined as the last non-missing measurement prior to the first dose of randomized IP. All statistical hypothesis tests will be performed at the 2-sided significance level of 5% for main effects. All confidence intervals (CIs) will be 2-sided 95% CIs, unless stated otherwise.

For efficacy analyses in which pooled study center is a factor, a small center will be defined as a center with < 2 patients in ≥ 1 treatment group in the mITT Population. Small centers will be pooled to form pseudo-centers so that each treatment group includes ≥ 2 mITT patients within the center. Pooling will be done using the following algorithm:

Based on the number of mITT patients, small centers will be ordered from the largest to the smallest, and centers of the same size will be ordered from the largest center code to the smallest center code. The pooling process starts with the largest small center from the top, which will be pooled with the smallest from the bottom until a non-small center is formed. The process will be repeated using the small centers left out after the first pass. If any centers are left out at the end of the process, they will be pooled with the smallest pseudo-center. If there is > 1 smallest pseudo-center, the pseudo-center with the smallest center code will be selected. In case the pseudo-center formed by pooling all small centers is still a small center, it will be pooled with the smallest non-small center. If there is > 1 smallest non-small center, the one with the smallest center code will be selected.

The efficacy analyses using the mITT population will be performed based on the treatment to which the patient is randomized regardless of the actual treatment received.

The efficacy analyses of MADRS assessments will be based on the rater-administered MADRS.

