11.3	VITAL SIGNS	The orthostatic hypotension was specified to be summarized for pre-dose, post-dose and other visits without IP administration separately for the DBTP.
13.0	INTERIM ANALYSIS	The blinded sample-size re-estimation was replaced by an unblinded interim analysis in order to identify early signs of futility.
14.0	DETERMINATION OF SAMPLE SIZE	The sample size estimation was revised to reflect a reduced significance level (from 0.05% to 0.049%) and associated power for the final primary efficacy analyses due to the addition of interim analysis.

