10.2 KEY SECONDARY EFFICACY PARAMETERS

The key secondary efficacy parameter will be the change from baseline in MADRS total score at 1 day after first dose of randomized IP. The key secondary efficacy parameter will be analyzed in the same MMRM model for the primary efficacy parameter. The treatment differences for rapastinel 450 mg versus placebo and rapastinel 900 mg versus placebo will be estimated and reported along with the corresponding 95% CIs and p-values.

[figure not shown]
Let H_1 and H_2 represent the treatment effect comparing rapastinel 450 mg versus placebo and rapastinel 900 mg versus placebo in regards to the primary efficacy parameter of change from baseline in MADRS total score at end of treatment (end of Week 6), respectively; and let H_3 and H_4 represent the treatment effect comparing rapastinel 450 mg versus placebo and rapastinel 900 mg versus placebo in regards to the secondary efficacy parameter of change from baseline in MADRS total score at 1 day after first dose of treatment. The graphical procedure displayed in Figure 10-1 will be employed to control the overall familywise error rate at $\alpha = 0.049$.

[figure not shown]
Figure 10-1

Graphical Testing Procedure

Specifically, H_1 and H_2 will be tested at $\alpha = 0.0245$ separately. If H_1 is rejected, H_3 will then be tested at $\alpha = 0.0245$. If H_2 is rejected, H_4 will then be tested at $\alpha = 0.0245$. If H_3 is rejected but H_2 is not rejected, H_2 will be further tested at $\alpha = 0.049$. If H_2 is rejected at $\alpha = 0.049$, H_4 will be further tested at $\alpha = 0.049$. Similarly, if H_4 is rejected but H_1 is not rejected, H_1 will be further tested at $\alpha = 0.049$. If H_1 is rejected at $\alpha = 0.049$, H_3 will be further tested at $\alpha = 0.049$.

[REDACTED]

[REDACTED]

[REDACTED]

[REDACTED].

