13.0 INTERIM ANALYSIS

An unblinded interim analysis will be conducted in order to identify early signs of futility. Separate Statistical Analysis Group and Data Review Committee will be established to conduct the unblinded interim analysis, review the unblinded results, and make recommendations regarding the continuation of the study. In order to maintain the scientific reliability of possible final results and guard from introducing any potential bias into the conduct of the study and/or analysis of its results, individuals in these 2 groups will not be involved in any operational aspect of the study. Additionally, to adjust for multiple comparison issues caused by having several looks at the data, the Bonferroni method will be applied to split the overall Type I Error between the interim and final analysis ($\alpha = 0.001$ and 0.049 two-sided, respectively) in order to further protect the integrity of the study. Further details of the unblinded interim analysis, in particular, its scope, the processes put in place to maintain study integrity, team structures, and responsibilities, are documented in the Data Review Committee Charter.

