14.0 DETERMINATION OF SAMPLE SIZE

This study initially planned to randomize approximately 690 patients to the rapastinel 450 mg, rapastinel 900 mg, and placebo groups in a 1:1:1 ratio. The primary efficacy endpoint is the change from baseline in the MADRS total score at the end of Week 6. Assuming the SD is 10 points, within-patient correlation is 0.6, and dropout rate over 6 weeks is 20%, a sample size of 230 patients per treatment group will provide 91% power to detect a difference of 3.5 points for each rapastinel dose versus placebo at a 2-sided significance level of 4.9% originally adjusting for multiple comparisons of 2 rapastinel groups with placebo across the primary and secondary endpoints by using a graphical testing procedure.

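### Does the general 5% test level in SAP Section 10.0 upset the 0.0245 and 0.049 levels that Section 10.2 sets for the primary and key secondary tests?

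*SAP*

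**What the plan says.** Section 10.0 sets general conventions for the efficacy analyses. On tests it says "All statistical hypothesis tests will be performed at the 2-sided significance level of 5% for main effects". On intervals it says "All confidence intervals (CIs) will be 2-sided 95% CIs, unless stated otherwise". The sentence on the analysis population in the same section also allows exceptions, so the testing sentence stands out for having none.

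Section 10.2 gives the confirmatory rule. H1 and H2 are the Week 6 comparisons of 450 mg and 900 mg with placebo. H3 and H4 are the matching Day 1 comparisons. A graphical procedure "will be employed to control the overall familywise error rate at" 0.049. The steps are then spelled out: "Specifically, H_1 and H_2 will be tested at $\alpha = 0.0245$ separately". H3 and H4 follow at 0.0245 once their parent hypothesis is rejected. If one dose succeeds at both time points, the other dose's hypotheses can be tested at 0.049.

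Section 13.0 explains the 0.049: "the Bonferroni method will be applied to split the overall Type I Error between the interim and final analysis", with 0.001 for the interim and 0.049 for the final analysis. Section 14.0 computes power "at a 2-sided significance level of 4.9" percent. The history of change (Section 3.0) records the same intent for Section 14.0: "The sample size estimation was revised to reflect a reduced significance level" for the final primary analyses because an interim analysis was added.

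**The concern.** A general rule that covers all tests and names 5% is untrue of H1 to H4, because none of them is assigned 5% at any step. The qualifier about main effects does not clearly exempt them, since they are treatment comparisons.

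The layout makes a misreading easier. Section 10.1, which describes the primary analysis, promises p-values and 95% intervals but gives no alpha and does not point to Section 10.2. The graph that governs the primary tests sits under the heading for the key secondary parameter. Someone who read only Sections 10.0 and 10.1 would find 5% and nothing else.

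The significance level of the confirmatory tests should be beyond dispute before unblinding. If 5% were applied to each dose on its own, the multiplicity control across the two doses would be lost.

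**Working it through.** **1. The plan's own alpha figures.**
- Across doses (Section 10.2): 0.0245 + 0.0245 = 0.049.
- Across looks (Section 13.0): 0.001 + 0.049 = 0.050.

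Both are exact. The 5% in Section 10.0 equals the total that Section 13.0 divides, and the 0.049 in Section 10.2 equals what is left for the final analysis.

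**2. The places side by side.**

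| Place in SAP | Level | Applies to |
|---|---|---|
| 10.0 | 5% | tests in general, for main effects |
| 10.2 | 0.0245, at most 0.049; familywise 0.049 | H1 to H4, by name and step |
| 13.0 | 0.001 and 0.049 | interim and final analysis |
| 14.0 | 4.9% | power for the primary endpoint |

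Three sections agree with one another. The one that differs is the general one, and it names no hypothesis.

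**3. Size of the plausible slip.** This is the Section 10.2 procedure run from 0.05 instead of 0.049, so 0.025 instead of 0.0245 per dose at the first step. Inputs from Section 14.0: SD 10, difference 3.5, 230 per arm, 20% dropout. Completers per arm are 230 × 0.8 = 184. The Week 6 information in the repeated-measures model lies between that of 184 and of 230 patients per arm.

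Standard error with 184 per arm: 10 × √(2/184) = 1.043. The critical difference is the standard error times the two-sided normal quantile, and power is Φ(3.5/SE − z).

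| Level | Critical difference, n = 184 | Power, n = 184 | Critical difference, n = 230 | Power, n = 230 |
|---|---|---|---|---|
| 0.05 | 2.043 | 0.9188 | 1.828 | 0.9635 |
| 0.049 | 2.052 | 0.9175 | 1.836 | 0.9628 |
| 0.025 | 2.337 | 0.8677 | 2.090 | 0.9347 |
| 0.0245 | 2.345 | 0.8660 | 2.097 | 0.9337 |

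The 91% in Section 14.0 is reproduced at 4.9% with 184 completers (0.9175). At 5% the figure is 0.9188, so the stated power does not depend on this point.

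At the first step the slip changes a given dose's result in 0.8677 − 0.8660 = 0.17% of trials with 184 per arm, and in 0.9347 − 0.9337 = 0.10% with 230. A simulation of the whole graph (2,000,000 draws) gives 0.15 to 0.17% and 0.08 to 0.10%. For at least one dose it gives 0.28 to 0.34% and 0.15 to 0.20%. The simulation assumes a correlation of 0.5 between doses from the shared placebo arm, Day 1 data on 230 per arm with SD 10, a Day 1 to Week 6 correlation of 0.3 to 0.6, and a Day 1 effect of 0, 1.5 or 3.5 points. The SAP gives no Day 1 effect.

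**4. Effect of that slip on total alpha.** The bound is 0.001 + 0.05 = 0.051. It applies only if efficacy can be claimed at the interim. Section 13.0 describes that look as a search for early futility and leaves further details to the Data Review Committee Charter. If no efficacy claim is possible there, the 0.001 is not spent and the final graph at 0.05 still keeps the familywise error within 0.05.

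**5. If Section 10.2 were ignored for H1 and H2.** With no effect of either dose and a correlation of 0.5, two tests at 5% each give a familywise error of 0.091, against 0.046 for two tests at 0.0245. This shows why the graph is needed. It does not describe what the plan would do, because the plan contains the graph.

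**The case for a change.** The strongest case for an edit is that the sentence is wrong as written, that its neighbours show the authors knew how to mark a default, and that a confirmatory plan should not rely on interpretation for its alpha. Adding an exception and a cross-reference would cost one line. The sentence also cannot be fully rescued by reading 5% as the overall error rate, because it states the level at which tests are carried out, not a total to be shared out.

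Most of this stands as a remark on drafting. The mismatch is real. The 5% may be a leftover from before the interim analysis was added, though that is an inference, since the earlier SAP is not available. What does not stand is the step from imprecise wording to an uncertain analysis. A generic convention yields to a rule that names the hypotheses and gives each one its level, and here that rule is supported by two other sections.

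The 5% default may also have a proper use. Text after the graphical procedure in Section 10.2 is blacked out, and efficacy tests outside H1 to H4 may rely on it. Only the missing exception can be faulted, not the presence of a default.

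**Conclusion.** No change to the plan is needed. The general sentence in Section 10.0 is loosely worded and does not fit H1 to H4, but the operative levels are fixed in Section 10.2 and confirmed in Sections 13.0 and 14.0. An edit would leave the data, the sample size, the programs and every confirmatory decision as they are.

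The realistic slip, 0.05 in place of 0.049 as the starting alpha, moves the first-step threshold by 2.345 − 2.337 = 0.008 points with 184 per arm. It alters a given dose's primary result in about 0.1 to 0.2% of trials. These figures rest on the Section 14.0 assumptions (SD 10, effect 3.5 points) and on Week 6 information worth between 184 and 230 patients per arm. The familywise error of 9.1% would need an analyst to disregard Section 10.2 altogether, which nothing in the SAP invites. If the SAP is reopened for another reason, an exception clause would tidy the sentence, but the point does not justify an amendment.

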10.1 PRIMARY EFFICACY PARAMETER

The primary efficacy parameter will be the change from baseline in MADRS total score at the end of treatment (end of Week 6). The MADRS contains 10 items that assess depression, with scores for each item ranging from 0 (absence of symptoms) to 6 (symptoms of maximum severity). The MADRS total score is the sum of the 10 individual items. If more than 2 items are missing, the total score will be set to missing. If there are multiple assessments of MADRS total score for the same day visit of a patient, only the last assessment will be used in the analysis.

The primary parameter will be analyzed using a mixed model for repeated measures (MMRM) with terms for treatment, pooled study center, visit (Day 1 visit and the weekly visits from Week 1 to Week 6), baseline, and treatment-by-visit and baseline-by-visit interactions. An unstructured covariance matrix will be used to model the covariance of within-patient scores. The Kenward-Roger approximation will be used to estimate denominator degrees of freedom (Kenward et al, 1997). This analysis will only use the observed postbaseline scores without imputation of missing values. The treatment differences for rapastinel 450 mg versus placebo and rapastinel 900 mg versus placebo will be estimated and reported along with the corresponding 95% CIs and p-values.

In the case that the MMRM model with unstructured covariance fails to converge with the default algorithm, then the Fisher scoring algorithm will be used to provide better initial values of the covariance parameters; if the model still does not converge, a simplified model without the factor of the pooled study center will be used to find the initial values of the covariance parameters. In the rare event that model still does not converge after using those initial values, simplified covariance structures will be used to fit the model in the following order until the model converges: (1) ante-dependence, (2) heterogeneous autoregressive, (3) Toeplitz, and (4) compound symmetry.

To assess the robustness of the primary MMRM results to the possible violation of the missing-at-random assumption, a sensitivity analysis will be conducted.

The sensitivity analysis will use a pattern-mixture model based on non-future dependent missing value restrictions (Kenward et al, 2003). The pattern for the pattern-mixture model will be defined by the patient's last visit with observed value. The observed MADRS total score at a visit is assumed to have a linear relationship with the patient's prior measurements. The missing values will be imputed under the assumption that the distribution of the missing observations differs from the observed only by a shift parameter value Δ . The dataset with observed and imputed values will be analyzed using the same model as the primary analysis for between-treatment group comparisons at the end of the treatment. The imputation of missing values and the analysis will be performed 20 times and the inference of this sensitivity analysis will be based on the combined estimates using the standard multiple imputation technique. The values of Δ will be selected as 0 to 8.

[figure not shown]

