4.0 INTRODUCTION

[figure not shown]
This statistical analysis plan (SAP) provides a more technical and detailed elaboration of the statistical analyses of the efficacy and safety data as outlined in the Study RAP-MD-32 protocol amendment 1 (dated May 22, 2019). Specifications of tables, figures, and data listings are contained in a separate document. The SAP for pharmacokinetic, pharmacodynamic and/or health economics and outcomes research data (if applicable) will be prepared separately.

Study RAP-MD-32 is a Phase 3, multicenter, randomized, double-blind, placebo-controlled, parallel-group study in patients 18 to 75 years of age who meet the Diagnostic and Statistical Manual of Mental Disorders, Fifth Edition (DSM-5) criteria for major depressive disorder (MDD). The symptoms and severity of MDD will be assessed based on their Montgomery-Åsberg Depression Rating Scale (MADRS) and Clinical [REDACTED]. All patients will be treatment naive (defined as those who have not received antidepressant, or have received antidepressant but not meeting adequate dose or duration criteria per the Antidepressant Treatment Response Questionnaire [ATRQ]) in the present episode or inadequate response (<50% reduction in depressive symptoms) to 1 to 3 antidepressant therapies (ADTs) given at adequate doses for ≥ 4 weeks during the present episode.

The study will include a total of 10 visits and will be approximately 10 weeks in duration:

- Up to 2-week screening period
- 6-week double-blind treatment period
- 2-week safety follow-up period (no treatment) for patients who do not roll over into the extension study

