Signed informed consent from the patient or the patient's legally authorized representative will be obtained before any study-related procedures are begun. Patients will wash out any previous ADT and/or prohibited medications during the screening period. Patients meeting the eligibility criteria at the end of Visit 2 will be randomized in a ratio of 1:1:1 to one of the three treatment arms: rapastinel 900 mg IV weekly, rapastinel 450 mg IV weekly, or placebo IV weekly. The double-blind treatment period (DBTP) starts with the first dose of study treatment. Upon completion of the DBTP, patients may be eligible to enter the extension study. Patients who do not enter the extension study will enter a 2-week safety follow-up period. Efficacy and safety assessments will be conducted at the clinic 1 day following the treatment day in the 1st week and at the ends of weeks 1, 2, 3, 4, 5 and 6 of the DBTP. Patients prematurely discontinuing from the study, regardless of cause, will be seen for a final evaluation. The schedule of evaluations for Study RAP-MD-32 is presented in [Table 4-1](#).

[figure not shown]

[figure not shown]

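### The primary and key secondary MMRM leaves out ATRQ prior-treatment status, a baseline factor that defines eligibility; the analysis stays valid but may give up a little precision

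*SAP*

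**What the plan says.** Section 4.0 defines two routes into the trial. The first is "treatment naive (defined as those who have not received antidepressant, or have received antidepressant but not meeting adequate dose or duration criteria", judged by the ATRQ for the present episode. The second is "inadequate response (<50% reduction in depressive symptoms) to 1 to 3 antidepressant therapies (ADTs") at adequate doses for at least 4 weeks in the present episode. Patients who meet eligibility at the end of Visit 2 are then "randomized in a ratio of 1:1:1 to one of the three treatment arms". The status is therefore fixed before treatment is assigned. The SAP text shown names no stratification factor.

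Section 10.1 gives the primary model as "terms for treatment, pooled study center, visit (Day 1 visit and the weekly visits from Week 1 to Week 6), baseline", with treatment-by-visit and baseline-by-visit interactions and an unstructured covariance matrix. Section 10.2 states: "The key secondary efficacy parameter will be analyzed in the same MMRM model for the primary efficacy parameter". All four hypotheses, H1 to H4, therefore rest on a model without prior-treatment status.

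Section 8.0 lists "Demographic parameters (age; race; ethnicity; sex), baseline characteristics (weight; height; and body mass index" for summary by treatment group in the mITT population. It also plans summaries of psychiatric history and of previous psychotropic medication by ATC code in the Safety Population. ATRQ status is not listed.

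**The concern.** The SAP already adjusts for baseline severity and center, and it sets out a detailed algorithm for pooling small centers. It does not use the one patient-level factor by which its own introduction describes who is enrolled. If naive patients and inadequate responders differ in mean MADRS change, that difference stays in the residual variance of all four tests.

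The visible baseline summaries would not show how the status is distributed across arms. A table of previous drugs by ATC class does not say whether dose and duration were adequate or whether response was below 50%. If the arms turned out to differ, an adjustment added afterwards would be post hoc.

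At stake is some efficiency, and the ability to see balance on an eligibility-defining factor.

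**Working it through.** **Inputs from the SAP (Section 14.0):** "Assuming the SD is 10 points, within-patient correlation is 0.6, and dropout rate over 6 weeks is 20"%; 230 patients per arm; difference 3.5 points; stated power 91% at a two-sided 4.9% level. Section 10.2 starts each dose at 0.0245.

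**Inputs assumed, because the SAP does not give them:** share p of one group, 0.2 to 0.5; difference d in mean Week 6 change between the groups after adjustment for baseline and center, 1 to 4 points. SD 10 is taken as the SD before adjustment for status.

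**Step 1, the plan's own figure.** Completers per arm: 230 × 0.80 = 184. SE = 10 × √(2/184) = 1.043. Power = Φ(3.5/SE − z):
- at 0.049: Φ(3.357 − 1.969) = 91.75%, which reproduces the stated 91%;
- at 0.0245: Φ(3.357 − 2.249) = 86.6%.

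A variant that credits the MMRM with partial data (compound symmetry, correlation 0.6, seven visits, linear dropout to 20%, effective n about 204 per arm) gives 90.0% at 0.0245 and 94.1% at 0.049. The gains below use 184 completers at 0.0245.

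**Step 2, variance explained by status.** R² = p(1−p)d²/100. The adjusted SD is 10 × √(1−R²).

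| p | d | R² | Power gain (percentage points) |
|---|---|---|---|
| 0.2 | 1 | 0.16% | 0.06 |
| 0.2 | 4 | 2.56% | 0.92 |
| 0.3 | 3 | 1.89% | 0.68 |
| 0.5 | 2 | 1.00% | 0.36 |
| 0.5 | 3 | 2.25% | 0.81 |
| 0.5 | 4 | 4.00% | 1.44 |

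At the top of the range, SE = 9.798 × √(2/184) = 1.022 and power is about 88.0%, against 86.6%.

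In patients, 690 × R²/(1−R²) gives about 7, 16 and 29 for d = 2, 3 and 4 at 50:50. That mix gives the largest R² for any d.

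**Step 3, chance imbalance.** The difference in shares between two arms of 230 has SD √(2p(1−p)/230). For p = 0.5 this is 0.0466, with a 95% limit of 9.1 percentage points; for p = 0.2 the limit is 7.3. Multiplied by d, the shift in the estimate runs from 0.073 × 1 = 0.07 to 0.0914 × 4 = 0.37 points, against the planned 3.5.

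**Step 4, is Step 3 an additional loss?** At p = 0.5 and d = 4 the shift has SD 4 × 0.0466 = 0.187. The unadjusted SE with 230 per arm is √(200/230) = 0.933. The squared ratio is (0.187/0.933)² = 4%, which is the R² of Step 2. In general, [2p(1−p)d²/n] / [2 × 100/n] = p(1−p)d²/100. The unadjusted standard error already contains the imbalance, so Steps 2 and 3 describe one quantity.

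**The case against.** The strongest case against is that nothing here is wrong. The model is fully specified, and randomization protects the comparison whether or not an optional covariate is included. One could equally propose sex, age or episode duration. No passage says that the two groups differ in outcome, and the assumed gain is small even at the favorable end. All of this stands, and it makes the point a low-priority improvement.

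A reader might infer more than the documents support:

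- **That the omission biases the result or inflates type I error.** It does neither; the arms are comparable by randomization.
- **That chance imbalance is a second harm on top of lost precision.** Step 4 of the working shows that it is the same one.
- **That a stratification factor is missing from the model, so that standard errors are too large.** The SAP names no stratification by this status, and the protocol is not at hand.
- **That these are two sharply separate populations, only one of which undergoes washout.** The naive group includes patients with some antidepressant exposure, and Section 4.0 has patients wash out any previous antidepressant therapy. Washout can occur in both groups.
- **That the plan as a whole ignores the status.** Text after Section 10.2 is redacted and could hold a subgroup or supportive analysis. Table specifications are also in a separate document. Neither alters the primary model, which is fully visible.

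What survives is narrow: the status is a pre-randomization value already needed for eligibility, the efficacy model does not use it, and using it would cost almost nothing.

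**Conclusion.** The omission is real and its effect is small. The planned analysis is valid under its own assumptions. It may give up precision worth about 0.2% to 4% of the variance, or about 0.1 to 1.4 percentage points of power per dose comparison. These figures rest on SD 10 from Section 14.0 and on an assumed mix of 20:80 to 50:50 and an assumed difference of 1 to 4 points. If the status does not predict change once baseline MADRS and center are in the model, the loss is essentially nil. The calculation is for Week 6; the SAP gives no separate planning figures for Day 1.

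**What to change.** Before unblinding, add ATRQ status (treatment naive versus inadequate response to 1 to 3 therapies) and status-by-visit as fixed effects in the Section 10.1 MMRM, and keep the same model for the Day 1 endpoint in Section 10.2. The interaction is needed because a main effect alone would force the same status difference at Day 1 and at Week 6. It parallels the baseline-by-visit term already planned. In Section 8.0, add the status to the baseline characteristics tabulated by treatment group.

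The cost is about seven fixed-effect parameters (one main effect and six for the interaction over seven visits), negligible with about 690 patients, and one table row. The data are already needed to establish eligibility. The downside is that there may be little or no gain if the status is not prognostic.
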